Justification for Number of Participants: We predict that there will be a medium effect size on parenting skills. A recent meta-analysis (Charach et al., 2013) reported an average effect size of .55 for proximal outcomes (i.e., parenting behaviors) and an average effect size of .75 for distal outcomes (i.e., child behaviors) for parent training studies. Prinz and colleagues (2021) recently reported that online, self-directed BPT was not inferior to in-person treatment, and self-directed parenting programs have been shown to produce medium, positive effects on child behavior (Baumel et al., 2017). Power analysis for the Aim 2 micro-randomized trial was conducted with R (version 4.1.3; MRTSampleSize package). With an estimated 28 days per family in the trial, randomization probability of 50% for receiving a micro-intervention, a decreasing linear trend of micro-intervention effects with a medium effect size, and constant availability estimated to be 60% (given targeted decision points), $n = 30$ families are needed (Liao et al., 2016), and we aim to recruit $n = 33$ to ensure sufficient power.

Characteristics of Participants: Study participants will consist of 33 families. Each family will include one child, ages 7-12, with ADHD and up to two caregivers (total of up to 99 people in the study). This population is justified as the treatment being evaluated aims to target parenting among parents of children with ADHD to improve parent skills, functioning, and child functioning. Childhood ADHD is a prevalent, persistent, and impairing disorder, and intervening may improve the outcomes for children with ADHD and their families. Similar interventions have been shown to be effective.

Inclusion and Exclusion Criteria: Inclusion criteria: 1) currently meets DSM-5 diagnostic criteria for ADHD, 2) ages 7 -12, 3) has parent or teacher-rated impairment in homework performance defined as a score of 3 or greater on an Impairment Rating Scale measure (Fabiano et al., 2006)

of homework performance, and 4) has at least one parent or primary caregiver who is willing to participate and is able to access the intervention at home via smartphone. Eligibility for participation will not be affected by current or past pharmacological treatment for ADHD or other diagnoses. Adverse events and changes in treatment will be assessed during monthly phone calls.

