Overview: This study is a micro-randomized trial (MRT) evaluating whether in-the-moment smartphone notifications (personalized parenting suggestions or personalized feedback) improve proximal parenting behavior among caregivers of children with ADHD. During up to two daily audio-recording sessions, caregivers are randomized every 6 minutes to: (a) no notification (50%), (b) suggestion (25%), or (c) feedback (25%). The proximal outcome is a binary indicator of positive parenting sentiment in the subsequent 6-minute window.

Primary Outcome: Binary indicator of positive sentiment (i.e., positive sentiment vs. negative or neutral sentiment) measured in the 6-minute epoch following each randomization decision point in the micro-randomized trial. Additionally, the binary indicator of negative sentiment measured in the 6-minute epoch following each randomization decision point will be examined as an outcome.

Primary Comparison: The marginal causal excursion effect of receiving any active micro-intervention (suggestion or feedback) versus no notification on the proximal binary outcome. Secondly, we will examine potential effects of micro-intervention type (feedback vs. suggestion/strategy) on sentiment.

Mean Differences: Means and standard deviations for outcome measures by micro-intervention condition are provided in clinicaltrials.gov.

Primary Analysis: A weighted, centered logistic regression model for binary proximal outcomes, implemented using the MRTAnalysis R package (D3C, University of Michigan). The model incorporates known randomization probabilities, participant-level clustering, and time-varying covariates as needed. Availability at each decision point will not be included in models as the participants have indicated availability by starting the recording (i.e., micro-interventions are only delivered within 30 minutes of participant starting audio-recording). The primary coefficient estimates the causal excursion log-odds ratio for active micro-intervention vs. no notification. Analyses are not aimed at determining significance given the small sample size and the pilot nature of the research study. Direction of effects, means, and user feedback and key outcomes.

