Secondary Analyses: Moderated causal excursion effects will examine whether treatment effects vary by factors that are static such as child age and oppositional defiant disorder symptoms at baseline, and time-varying moderators including progress in asynchronous treatment (i.e., behavioral treatment modules) and sentiment immediately prior to randomization. All secondary analyses are exploratory.

Missing Data: Decision points without valid audio or outcome coding will be excluded from primary analyses. Sensitivity analyses will be conducted including only micro-intervention instances in which users confirmed micro-intervention receipt on their phone (as well as the no micro-intervention condition). Given availability, missingness is low.

Software: All analyses will be performed in R, using the MRTAnalysis package for estimation of marginal and moderated causal excursion effects for binary proximal outcomes.

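### If notification effects fade over the 28 days, as the sizing assumes, the exploratory module-progress moderator cannot separate module progress from time in study unless treatment × day is fitted with it

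*Combined protocol and SAP*

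**What the plan says.** - **Moderator.** Secondary Analyses in the SAP lists "progress in asynchronous treatment (i.e., behavioral treatment modules" as a time-varying moderator, together with sentiment just before randomization, after static factors such as child age. It adds: "All secondary analyses are exploratory". Study day does not appear.
- **Calendar.** Methods and Activities, item 5, gives families a 4-week version of the module programme during the same four weeks as the notifications. Duration of Participation describes weekly engagement over those weeks.
- **Assumed course of the effect.** Justification for Number of Participants begins "With an estimated 28 days per family in the trial" and assumes "a decreasing linear trend of micro-intervention effects with a medium effect size". It does not say in words that the trend runs over study day, but no other time scale is mentioned.
- **Covariates.** Primary Analysis allows "time-varying covariates as needed" and names none. No treatment × day term appears anywhere in the SAP.
- **Inference.** Primary Analysis disclaims significance testing and appears to name direction of effects among the key outcomes.

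**The concern.** Notifications are randomized; module progress is not. Cumulative progress rises with the calendar, and the plan's own sizing has the effect fall along that calendar. A treatment × progress model without treatment × day has only progress through which to express a decline over time. The report could then say that notifications help less once parents have worked through the modules when they have simply worn off, or could miss that modules strengthen them. These readings point to different design choices, and the Overview gives Aim 2 the job of refining the intervention and deciding which micro-interventions to keep. Because the SAP reads direction rather than significance, a wrong sign is the error that matters.

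**Working it through.** **The plan's own figure.** The sizing gives 30 families needed and 33 to recruit. I used the standard micro-randomized-trial formula: a noncentral F with 2 and N − q − 2 degrees of freedom (q = 2 or 3) and noncentrality N × 0.6 × 0.5 × 0.5 × Σd(t)², where 0.6 is the assumed availability and 0.5 comes from "randomization probability of 50% for receiving a micro-intervention". The standardized effect, alpha, power and decision points per day used in the sizing are not stated, so 30 can be neither confirmed nor refuted. With 9 points per day, two-sided alpha 0.05 and an assumed mean effect of 0.10, N is 27 (80% power) or 35 (90%) if the effect starts at 1.5 times its mean, and 23 or 29 if it declines to zero. Nothing below depends on this.

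**Why the slope moves.** Put study day u and module progress p on 0 to 1 scales. Let the notification log-odds ratio be F(1 − u) + γp, where γ is the true module effect. Leaving out treatment × u gives approximately

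progress-only slope ≈ γ − F × b,

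where b is the regression coefficient of u on p.

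**Logistic simulation.** From the documents: 33 families, 28 days, up to 9 decision points per day, 50% active. Assumed: F = 0.8 (the log-odds ratio falls from 0.8 to 0, mean 0.4), γ = 0, and three patterns of module pace. The model is action-centred logistic with 400 replicates per scenario. At 9 points per day, slopes are in log-odds ratio per full programme:

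| Pace | Corr(p, u) | Progress-only slope | Negative | Slope with treatment × day | Negative | SE, progress-only → joint |
|---|---|---|---|---|---|---|
| Strict weekly | 0.97 | −0.79 | 100% | −0.04 | 51% | 0.158 → 0.641 |
| Self-paced with drop-off | 0.62 | −0.45 | 100% | +0.02 | 49% | 0.155 → 0.184 |
| Very uneven | 0.41 | −0.26 | 98% | −0.005 | 50% | 0.126 → 0.131 |

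Variations, always in the order weekly, self-paced, uneven:
- *5 points per day:* negative in 100%, 99% and 95%.
- *Half the effect (mean 0.2), 9 per day:* slopes −0.39, −0.24 and −0.14; negative in 99%, 94% and 86%.
- *No fade:* slopes within about 0.01 of zero in all patterns. The fade is the cause.
- *Day as a main effect only:* slopes −0.79, −0.46 and −0.26, essentially unchanged. Such a covariate adjusts the level of the outcome, not the treatment effect.
- *True strengthening, γ = +0.4:* the formula predicts 0.4 − 0.79 = −0.39, 0.4 − 0.45 = −0.05 and 0.4 − 0.26 = +0.14; the simulation gave −0.39, −0.09 and +0.13. The sign was wrong in 99.5%, 72% and 18% of replicates. With treatment × day fitted, the slopes were +0.37, +0.39 and +0.39, and the sign was wrong in 29%, 3.5% and 0%.

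**Linear-model simulation.** This used 33 × 28 × 9 decision points with 60% available, and assumed 40% positive windows, 0 to 4 self-paced modules and a progress-day correlation of 0.80. With no module effect and a decline from +12 to 0 percentage points, the progress-only slope averaged −2.2 points per module, against about 0 with day and treatment × day. With a true +2 points per module and a decline from +10 to 0, it averaged about +0.15 (wrong sign in 47% of trials), against +1.96 (12%) in the joint model. The standard error rose from about 1.1 to 1.7 points per module.

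**The case against.** The strongest reply is that the listed analysis is not in error. A moderated causal excursion effect is averaged over whatever is left out of the moderator set. If notifications fade while progress rises, the effect really is smaller at higher progress, and the progress-only slope estimates that correctly. **This stands.** A reader might infer that the plan yields a biased slope; the documents do not support that, since Secondary Analyses asks only whether effects vary by progress and makes no claim that modules cause the variation. The weakness lies in interpretation. Even with day in the model, progress remains confounded with family engagement.

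Other points on that side:
- **The fade is a sizing input, not a result.** This stands; without it there is no distortion.
- **The SAP does not exclude day.** Its moderator list is open-ended, it does not say whether moderators are fitted singly or jointly, and it allows covariates as needed. This stands in part. Treatment × day is not ruled out, but it is not named either, and day as a covariate alone would not help.
- **The analysis is exploratory.** True, and it limits the weight of the point. But direction is what the SAP proposes to read, and direction is what is at risk.
- **The consequences can be overstated.** A reader might infer that the progress slope will set the Aim 3 tailoring rules. The Overview assigns tailoring variables and decision rules to Aim 1; Aim 2 is to refine the intervention and choose its micro-interventions.

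**Conclusion.** The point holds as an inexpensive improvement to an exploratory analysis, not as an error in the plan. If the effect fades over study day, the progress-only slope cannot distinguish module progress from elapsed time. With no true module effect it was negative in 86% to 100% of logistic replicates, and a genuine strengthening of +0.4 was reversed on average in two of the three pace patterns.

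This rests on reading the sizing trend as running over study day, on the fade actually occurring, and on assumed effect sizes and module pace. The direction of the distortion follows from the design; its size cannot be fixed from the documents. It would also be wrong to infer that the primary comparison is biased: the treatment × progress term plays no part in it.

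**What to change.** In Secondary Analyses:

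1. List study day (centred) as a time-varying moderator. This also checks the decline assumed in the sizing.
2. Report the module-progress model with day and treatment × day fitted jointly with treatment × progress, beside the progress-only slope. Label the latter as a marginal description.
3. Report the correlation between progress and study day.
4. State that if families keep to a near-weekly pace, the report will say the two cannot be separated.

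Adding day to the primary model is not needed for this problem.

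The cost is a few lines of SAP text and no new data, since study day is already recorded. The price is precision. In the logistic simulation at 9 points per day, the standard error rises by about 4% with very uneven pace (0.131/0.126), about 19% if self-paced (0.184/0.155) and about fourfold at a strict weekly pace (0.641/0.158). In the last case even the joint model had the wrong sign in 29% of replicates with a true +0.4, which is why item 4 is needed.
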